12. EFFICACY ENDPOINTS, SAFETY, PHARMACOKINETIC, AND OTHER ASSESSMENTS

12.1. Efficacy Endpoints

Efficacy endpoints include the following:

- Exercise testing using CPET (peak workload and VO₂MAX)
- T1MW and T25FW
- Speech measurement recording
- Clinician-rated Scales
 - o FARS-Neuro
 - Clinician-rated CGI
- Questionnaires and scales completed by the subject
 - o FARS-ADL
 - o SF-36
 - Patient Global Impression of Change (PGI-C)
 - o VAS
 - Fatigue scale
 - o Neuro-QoL scale (lower extremity function and upper extremity function)
 - o Fall Questionnaire
 - Speech Assessment Questionnaire
- Frequency of falls, near falls, and stumbles as reported in a fall diary

12.2. Exercise Testing Using CPET

Subjects will perform exercise testing using the CPET protocol at Screening, on Day 1, Day 120 (\pm 30 days), Day 240 (\pm 30 days), and Day 330 (\pm 30 days). Peak work rate and VO₂ MAX will be measured during incremental exercise testing on a recumbent bike. All tests should be done at approximately the same time for each visit. CPET should occur after fasting (if the subject has had a meal/snack) for a minimum of 2 hours, with neither caffeine nor nicotine for at least 12 hours before testing. Fluid consumption during the fasting period is limited to water, preferably at room temperature. Physical activity during the 24 hours prior to testing should be minimized. Routines followed for the initial laboratory assessments with respect to diet and physical activity should be duplicated for each subsequent visit. Subjects may take as much resting time as they

need between the bike test and the T1MW/T25FW. Detailed testing instructions will be provided in a separate manual.

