	12. History, within the last 2 years, of alcohol abuse, significant mental illness, or physical opioid dependence
Food Journal requirement	While on study drug, subjects are recommended to avoid eating foods high in PUFAs. Subjects will keep food journals from screening through the completion of month 1 on study drug. After month 1, subjects will keep 2-week food journals prior to next scheduled onsite visit. Subjects (or parents/caregivers, as applicable) will have an initial call and as needed with the diet coach to discuss food journal completion requirements.
Prohibited Medications	Supplements that contain EPA or DHA are prohibited. Oil-based supplements like Fish oil, Cod Liver oil, Edible algae oil and Flax oil are also prohibited.
Statistical methods	Demographic data will be presented using descriptive statistics (e.g., mean, standard deviation, median, and range). Exposure to study drug and reasons for discontinuation will be tabulated. Safety variables will be tabulated and presented for all subjects who receive study drug or placebo capsules. Adverse events will be coded using the Medical Dictionary for Regulatory Activities (MedDRA). The incidence of treatment-emergent AEs will be presented by system organ class and preferred term. Adverse events will be presented by severity and relationship to

study drug. Changes from Baseline in clinical laboratory parameters and vital signs will be summarized across time. Shift tables will be provided for selected laboratory parameters. Physical examination results will be presented in listings.

Change from baseline (CFB) will be analyzed by comparing the change between treatment groups using a mixed model with repeated measures (MMRM). The MMRM will compare the estimated change from baseline between treatments for the primary endpoint. This analysis will assess whether there is a difference in estimated CFB between active and placebo groups at 11 months.

The primary analysis of percent change from baseline to 11 months in MVO2 as measured by CPET will use the ITT methodology and an MMRM methodology with a random slope and intercept for each individual.

All secondary and exploratory endpoints CFB values will be analyzed using the MMRM Responder analyses will be run on MVO2 (primary), GST, T1MW, Peak Workload, mFARS, and CGI-C (functional assessment). The PK of D2-LA, D2-ARA, H2-LA, and H2-ARA will be characterized in terms of minimum and maximum exposure at steady state.

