7.1. Primary endpoint

1. To demonstrate the efficacy of RT001 compared to placebo on the change of MVO2 in patients with FA through change from baseline to 11 months

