12.3. Timed Walk

12.3.1. Timed 1-Minute Walk (T1MW)

The T1MW is a quantitative measure of lower extremity function. The subject is instructed to walk for 1 minute as quickly and safely as possible on a clearly marked course. The distance walked over 1 minute is measured. The T1MW will be performed on subjects who are ambulatory (with or without assistive device). This will be evaluated at Screening, on Day 1, Day 120 (\pm 30 days), Day 240 (\pm 30 days), and Day 330 (\pm 30 days).

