13.1. Visit 1: Screening (Up to 30 Days)

Screening procedures can be performed from 30 to 14 days prior to the first dose on Day 1. A signed and dated ICF (or assent form) will be obtained from the subject as required by the protocol before any screening procedures are conducted. A signed copy of the ICF will be given to the subject. Screening procedures include the following:

- Evaluate eligibility per inclusion/exclusion criteria
- Perform a serum pregnancy test for all female subjects, unless there is documented evidence confirming they are not of childbearing potential
- Obtain blood samples for hematology, chemistry, coagulation, and lipid profile in a fasting state
- Obtain a urinalysis sample (dipstick test and microscopic examination if clinically indicated)
- Perform the exercise bike test (CPET should occur in the morning after fasting for a minimum of 2 hours {if the subject has had a meal/snack}, with neither caffeine nor nicotine for at least 12 hours before testing)
- Perform a FARS-Neuro and clinician-rated CGI (severity of illness question only)
- Record medical history and demographics
- Record the C-SSRS
- Complete the Speech Measurement Recording
- Perform a physical examination
- Record vital sign measurements, height, weight, and BMI
- Subject complete FARS ADL, SF-36, VAS (for Fatigue), Fatigue scale, Neuro-QoL scales, Speech Assessment Questionnaire and Fall questionnaire

- Obtain T1MW and T25FW
- Obtain an echocardiogram (LVEF) (To be performed if there has been no echocardiogram performed in the last 12 months before screening).
- Obtain a 12-lead ECG
- Sites to train subject on completion requirements for the Fall Diary
- Phone call with the diet coach to review food journal completion requirement

13.2. Visit 2: Study Day 1

The following procedures will be performed:

Pre-Dose

- Reassess inclusion/exclusion criteria
- Obtain blood samples for hematology, chemistry, coagulation, and lipid profile in a fasting state (does not have to be repeated if Screening visit is ≤ 7 days and there are no clinically significant findings)
- Perform a urine pregnancy test for all female subjects unless there is documented evidence confirming they are not of childbearing potential
- Perform the exercise bike test (CPET should occur in the morning after fasting for a minimum of 2 hours {if the subject has had a meal/snack}, with neither caffeine nor nicotine for at least 12 hours before testing)

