- Perform a FARS-Neuro and clinician-rated CGI (severity of illness question only)
- Update medical history and demographics
- Complete the Speech Measurement Recording
- Record vital sign measurements and weight
- Obtain blood samples for biomarkers prior to the morning meal and dosing
- Randomize subject to study treatment group and dispense study drug
- Perform a physical examination
- Subject complete FARS ADL, SF-36, VAS (for Fatigue), Fatigue scale, Neuro-QoL scales, Speech Assessment questionnaire and Fall questionnaire
- Obtain T1MW and T25FW
- Obtain a 12-lead ECG (does not have to be repeated if Screening visit is ≤ 7 days and there are no clinically significant findings

Collect fall diary

Dosing

Subjects will take, as per the randomization scheme, the first dose of study drug at the clinic with a meal after all baseline testing is complete.

Post-Dose

- Record concomitant medications
- Record AEs

13.3. Days 30 (\pm 7 days), 60 (\pm 7 days), and 90 (\pm 7 days)

Subjects will be contacted by phone by a study site staff member and asked to complete the PGI-C, the Fatigue scale, the Neuro-QoL scales (lower extremity function and upper extremity function), and questions 8 and 9 of the Fall questionnaire. Subjects can scan and email questionnaires to the site. The site is to also confirm if the subject is taking study drug as instructed. Adverse events will also be assessed.

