Change from baseline (CFB) will be analyzed by comparing the change between treatment groups using a mixed model with repeated measures (MMRM). The MMRM will compare the estimated change from baseline between treatments for the primary endpoint. This analysis will assess whether there is a difference in estimated CFB between active and placebo groups at 11 months.

The primary analysis will use the ITT methodology and an MMRM methodology with a random slope and intercept for each individual. Due to the small sample size the model will be optimized by implementation of two risk scores (baseline and slope) that account for multiple baseline covariates in one variable. The risk scores will be derived from blinded data using the GST change from baseline values and generated using the baseline model covariates (excluding treatment and visit; baseline risk score) or the baseline model covariates*time interactions (slope risk score). The risk scores will be included as covariates in the model.

To calculate the baseline risk score, the GST change score is regressed on the covariates listed below. Individual coefficients for the baseline risk score are multiplied by individual covariate values and summed. A separate slope risk score is calculated for baseline covariates interacting with time.

The MMRM with primary outcome CFB value as the response variable will include the following covariates and fixed effects:

- baseline risk score:
 - baseline score for GST
 - age
- slope risk score:
 - baseline score for GST * time
 - age*time
- Time (continuous)
- Time by treatment interaction (time*treatment)
- baseline score for parameter of interest (if not in GST)
- site pooled by region (random effect)

Model assumptions will be evaluated. If the parametric assumptions are evaluated as inappropriate or violated, rank analogues will be advanced.

All secondary and exploratory endpoints CFB values will be analyzed using the MMRM described above. This analysis will assess whether or not there is a difference in estimated CFB values between treatment group and placebo at the 11-month model estimate using least squares means estimates from the MMRM model.

Speech measurement reporting will be analyzed by a third party vendor. A separate report will be provided.

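### MVO2, peak workload and T1MW are each measured twice before dosing, but section 14.1 neither says which value is baseline nor provides for using both

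*Combined protocol and SAP*

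**What the plan says.** Section 12.2 schedules the exercise test, which yields MVO2 and peak workload: "Subjects will perform exercise testing using the CPET protocol at Screening, on Day 1, Day 120" and at the later visits. Section 12.3.1 says of the 1-minute walk: "This will be evaluated at Screening, on Day 1, Day 120", again with later visits. Table 1 and sections 13.1 and 13.2 agree. On spacing, section 13.1 states: "Screening procedures can be performed from 30 to 14 days prior to the first dose on Day 1". A footnote to Table 1 also allows for Screening and Day 1 falling within 7 days of each other.

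Section 7.1 sets the primary objective "on the change of MVO2 in patients with FA through change from baseline to 11 months". The synopsis uses a different scale: "The primary analysis of percent change from baseline to 11 months in MVO2 as measured by CPET". In section 14.1, "The MMRM will compare the estimated change from baseline between treatments for the primary endpoint", and "The primary analysis will use the ITT methodology and an MMRM methodology with a random slope and intercept for each individual". The listed covariates are the baseline and slope risk scores (built from baseline GST and age), time, time by treatment and pooled site. The baseline of the endpoint itself is added only for endpoints outside the GST. Section 7.2 lists the GST components as T1MW, peak workload and MVO2.

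No section defines the efficacy baseline. The nearest hint is in section 13.2, where the first dose on Day 1 is taken "at the clinic with a meal after all baseline testing is complete". That describes the order of procedures and is not an analysis definition.

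**The concern.** Two things are at stake.

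The first is that the primary response is not fully specified. Screening, Day 1 and the mean of the two give three different change scores, three different GST baselines and three different sets of risk scores. The choice should not still be open when treatment codes become available.

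The second is precision. If one test serves as baseline, its measurement error enters all three post-dose change values of that subject. A model that conditions on the endpoint's own baseline removes part of this error. Here MVO2, peak workload and T1MW have no such term, and only the composite GST baseline enters, through the risk scores. A second pre-dose test is already being collected and could reduce the error. With 60 subjects, and with no SD or power given for MVO2, that is worth having.

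**Working it through.** **Inputs from the documents.** Two pre-dose tests; post-dose tests at Months 4, 8 and 11; 30 per arm; difference 15.8 and SD 11.1 for peak workload; two-sided alpha 0.05 (sections 12.2, 12.3.1, 14.2 and the synopsis).

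**Inputs that have to be assumed.** r, the correlation of a pre-dose test with Month 11; r0, the correlation of Screening with Day 1; and the share of the Month 11 change variance that is due to true differences in slope. The comparator is taken to be Day 1 alone. Screening and Day 1 are given equal variance and equal correlation with Month 11.

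**The plan's own figure.** 30 per arm, difference 15.8, SD 11.1: power is 0.9997 (noncentral t) or 0.9998 (normal approximation). The stated figure of over 99% reproduces, for peak workload.

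**1. Simple change at Month 11.** Variance ratio, mean of two against one = [1 + (1 + r0)/2 − 2r] / (2 − 2r).
- r0 = r: 0.75, a 25% reduction (on the peak workload scale, SD 11.1 × √0.75 = 9.61).
- r = 0.9, r0 = 0.95: 0.875, 12.5%.
- r = 0.8, r0 = 0.95: 0.9375, about 6%.
- r = 0.5, r0 = 0.95: 0.975, 2.5%.

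**2. Month 11 adjusted for the endpoint's own baseline.** Variance ratio = [1 − 2r²/(1 + r0)] / (1 − r²).
- r = r0 = 0.9: 0.776, about 22%.
- r = r0 = 0.6: 0.859, about 14%.
- r = 0.5, r0 = 0.95: 0.991, about 1%.

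**3. Simplified form of the planned model.** Change at Months 4, 8 and 11 with common intercept, time, and time by treatment; risk scores and site are left out. The covariance of a subject's three changes is V = σ²(slope)·tt′ + σ²(error)·I + σ²(base)·11′, with σ²(base) = σ²(error) for one test and half that for the mean of two. The variance compared is that of the time by treatment effect at 11 months, by generalised least squares.

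| Slope share of Month 11 change variance | Slope variance at Month 11 ÷ error variance | Variance reduction | Equivalent extra subjects |
|---|---|---|---|
| 0% | 0 | 28% | 38% |
| 25% | 0.67 | 20% | 25% |
| 50% | 2 | 13% | 15% |
| 75% | 6 | 6% | 7% |
| 90% | 18 | 2.5% | 2.5% |

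**4. Screening as the only added covariate.** With unit variances, Cov(Month 11 − Day 1, Screening) = r − r0. This is zero when r0 = r, so adding Screening alone to a Day 1 change score then gains nothing. With r = r0 = 0.8 the residual variance is:
- Day 1 change, no covariate: 2 − 2(0.8) = 0.40.
- Screening added: 0.40 − 0² = 0.40.
- Day 1 added: 1 − 0.64 = 0.36.
- Both added: 1 − 2(0.64)/1.8 = 0.289.

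**5. A noisier Screening test.** If Screening error variance is k times that of Day 1, with independent errors, the mean has error variance (1 + k)/4 of the Day 1 error. This is 0.50 at k = 1 and 0.75 at k = 2, and reaches 1 at k = 3. The gain shrinks as k grows and is gone at k = 3.

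**Effect on stated power.** At a difference of 15.8, power stays above 99.9% either way. The difference detectable with 80% power (peak workload scale) falls from 8.2 to 7.1 with a 25% reduction, or to 7.9 with a 6% reduction.

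**The case against.** The strongest reply is that nothing has been given up. A reader might infer that the plan uses one test and discards the other, but the text never says so. An undefined baseline leaves averaging open, and section 14.1 defers full detail to a separate statistical analysis plan, to be finalised before unblinding, that is not in the supplied documents. This stands: the supportable finding is a missing definition and a missing provision for the second test. It does not remove the point, because section 14.1 already fixes the covariates and omits the own-baseline term for GST components, which is what makes the choice of baseline matter.

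A reader might also infer that baseline error is shared across visits and so cannot be averaged out by more follow-up. That holds for a simple Month 11 change score but not for the planned model, where the random intercept absorbs shared error and the within-subject slopes are free of it. In the simplified model, with slope variance 0 to 2 times error variance, the gain from averaging is 28% to 13% with three visits, 16% to 5% with eleven monthly visits and about 6% to 1% with 44. The loss is real with the three visits planned here, but it is not irreducible.

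A confident figure of 13% to 28% is tempting as well. It rests on slope differences making up no more than half of the Month 11 change variance, for which the documents give no basis. Tests a few weeks apart would also ordinarily correlate more strongly than tests 11 months apart in a progressive disease, which lowers the gain. The risk scores contain baseline GST and will remove some of the error. As a bound, had they adjusted fully for own baseline, the gain at test-retest correlation 0.6 to 0.9 would be about 19% to 26% with no slope variance and 8% to 12% at twice the error variance.

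A practice effect between the two tests does not bias the contrast: both precede dosing, and exclusion 5 is inability to complete the test rather than a numeric cut-off. It does affect precision if it varies between subjects.

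Finally, stated power is over 99% regardless. That calculation is for peak workload, and the documents give no equivalent for MVO2.

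**Conclusion.** The point holds as a gap in specification with a precision benefit attached. Two pre-dose values exist for MVO2, peak workload and T1MW; section 14.1 does not say which is baseline or how both could be used; and its covariate list would let single-test error pass into the primary contrast. Relative to Day 1 alone, averaging lowers the variance of the Month 11 contrast by roughly 1% to 28%. The upper end needs negligible true slope variation. The lower end applies when Screening and Day 1 agree far more closely with each other than with Month 11, or when slope differences dominate. The documents contain no MVO2 SD, test-retest correlation or slope variance that would narrow this range. The definition is needed whatever the gain turns out to be.

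**What to change.** In section 14.1, before unblinding, define baseline for MVO2, peak workload and T1MW as the mean of the Screening and Day 1 values, or the single available value if one is missing. Use the same definition for the GST baseline and the risk scores.

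If the sponsor prefers Day 1 for the change score, keep it and add both the Day 1 and the Screening values of that endpoint as covariates. Screening alone is not enough (step 4 above). This option lets the data weight the Screening test if it is the noisier one.

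The cost is wording, since both tests are already scheduled. Averaging shifts within-arm mean change slightly if there is a practice effect, and rescales the between-arm contrast slightly if percent change is the response, so the scale should be settled at the same time. A practice effect that varies between subjects shrinks the gain. The covariate option costs one or two degrees of freedom.

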12.3. Timed Walk

12.3.1. Timed 1-Minute Walk (T1MW)

The T1MW is a quantitative measure of lower extremity function. The subject is instructed to walk for 1 minute as quickly and safely as possible on a clearly marked course. The distance walked over 1 minute is measured. The T1MW will be performed on subjects who are ambulatory (with or without assistive device). This will be evaluated at Screening, on Day 1, Day 120 (\pm 30 days), Day 240 (\pm 30 days), and Day 330 (\pm 30 days).

12.3.2 Timed 25-Feet Walk (T25FW)

The T25FW is a quantitative measure of lower extremity function. The subject is instructed to walk 25 feet as quickly and safely as possible. The time to walk 25 feet will be measured electronically. The T25FW will be performed on subjects who are ambulatory (with or without assistive device). This will be evaluated at Screening, on Day 1, Day 120 (\pm 30 days), Day 240 (\pm 30 days), and Day 330 (\pm 30 days). Detailed testing instructions will be provided in a separate manual.

12.4. Speech Measurement Recording

The subject will have to undergo a speech recording for about 10 minutes at Screening, on Day 1, Day 240 (\pm 30 days), and Day 330 (\pm 30 days). This recording will include (but not limited to) (1) reading a brief passage, (2) responding to a task: e.g. days of the week (3) syllable repetition: e.g. saying PATAKA as quickly and as clearly as possible; (e) monologue: on a topic of choice. Details will be included in a separate manual.

12.5. Clinician-rated Scales

12.5.1. FARS-Neuro

The FARS-Neuro scale includes evaluations of the neurological signs that specifically reflect neural substrates affected in subjects with FRDA. Based on a neurological examination, bulbar, upper limb coordination, lower limb coordination, peripheral nervous system, and upright stability functions are assessed for individual sub-scores (11, 36, 16, 26, and 36) with a maximum score of 125 (Friedreich's Ataxia Study Group, Subramony et al., 2005, Lynch et al., 2006). FARS-Neurologic examinations will be conducted by a qualified physician or health professional listed on the Form FDA 1572 who is trained on use of the FARS-Neurologic scale format. This scale will be evaluated at Screening, on Day 1, Day 120 (± 30 days), Day 240

(\pm 30 days), and Day 330 (\pm 30 days). The CPET examination should always precede the FARS-Neuro evaluation at all visits. Refer to Section 19.2 for the specific items assessed.

12.5.2. Clinician-rated Clinical Global Impression (CGI)

The CGI is a 3-item observer-rated scale that measures illness severity, global improvement and therapeutic response. The illness severity is rated on a 7-point scale, with the severity of illness scale using a range of responses from 1 (normal) through 7 (amongst the most severely ill patients). The global improvement scores range from 1 (very much improved) through to 7 (very much worse). Treatment response ratings should take account of both therapeutic efficacy and treatment-related adverse events and range from 0 (marked improvement and no side-effects) and 4 (unchanged or worse and side-effects outweigh the therapeutic effects). Each component of the CGI is rated separately; the instrument does not yield a global score. This scale will be evaluated at Screening, on Day 1, Day 120 (\pm 30 days), Day 240 (\pm 30 days), and Day 330 (\pm 30 days). At screening and Day 1, only the severity of illness (question 1) needs to be assessed. From Day 120 onwards, all 3 items (severity of illness, global improvement, and therapeutic response) will be assessed. Refer to Section 19.3 for the specific items assessed.

